## **Objectives:**

This pilot effectiveness trial aims to determine the impact of the Crowd-Powered Platform on symptoms of depression and anxiety and evaluate whether the platform engages the putative targets of personal relevance and interpersonal relationship building, resulting in increased skills mastery and skills use. We will enroll 100 participants in a two-armed randomized controlled trial of the platform. Participants will be randomly assigned to receive either the crowd-powered platform (treatment) or a similar self-guided platform (control) that contains the didactic material (learning) but none of the crowd features. Participants will be recruited from Mental Health America (MHA)'s Screening-to-Supports platform, an online screening platform that conducts approximately 3000 screens each day. The MHA Screening-to-Supports platform includes screeners for depression (PHQ-9) and anxiety (GAD-7). Individuals who screen positive for depression or anxiety will receive brief online study advertisements. Study advertisements will be 1-2 sentences long, and include the following text: "Click here to take part in a 16 week paid trial and test a new online platform for depression and anxiety". Individuals who receive and click on these advertisements will have access to a REDCap form with screening questions regarding demographics, contact information, age, diagnostic status and English proficiency. Those who are eligible as determined by the web screener will be contacted by research personnel to schedule a 1 hour remote interview where they will 1) review the consent form with research staff and electronically sign via REDCap's e-consent form 2) complete a diagnostic assessment with modules of the SCID. Afterward, participants will be sent a REDCap link via email to complete baseline assessments and will receive login information for their assigned platform (e.g., treatment or control) via email. Participants will use their assigned platform for 8 weeks and will be instructed to use the platform at least 3 times per week. Participants will be sent weekly newsletters via Mailchimp.com, and text message reminders to complete surveys. These newsletters will include didactic information about the platform and platform content, reminders to engage with the platform, and reminders to complete study measures. Participants will receive trial assessments at baseline, week 4, and week 8 (post-treatment). Follow-up evaluations will occur at 16 weeks to evaluate maintenance of gains. In addition, a subset of participants will be asked to complete a one-hour evaluation of user experience at 16 weeks.

## **Design:**

100 participants will be enrolled in a two-armed randomized controlled trial of the ADAPT platform. Participants will be randomly assigned to receive either the ADAPT platform (treatment) or a similar self-guided platform (control) that contains the didactic material (learning) but none of the crowd features (requesting or responding). Participants will use their assigned platform for a treatment period of 8 weeks. Participants will receive trial assessments at baseline, week 4, and week 8 (post-treatment). Follow-up evaluations will occur at 16 weeks to evaluate maintenance of gains.

## **Methods:**

Participants will be asked to interact with their assigned platform for 8 weeks, at least 3 times per week. Each platform interaction is estimated to take between 5-10 minutes, but participants may choose to engage on the platform for as long as they would like. Participants will be randomized into one of two conditions, where they may either interact with a version of this platform that includes content intended to teach you about mental health and skills, or a similar version that also includes peer support. Participants will be asked to complete an initial, one-time mental health assessment via Zoom call that will take approximately one hour. Participants will be sent weekly newsletters via Mailchimp.com. These newsletters will include didactic information about the platform and platform content, reminders to engage with the platform, and reminders to complete study measures. Email addresses will be used to send participants newsletters through Mailchimp.com. No additional identifying information will be shared with Mailchimp.com. Subjects may unsubscribe from Mailchimp

newsletters at any time. When the study is complete, the contact list of subject emails will be deleted from Mailchimp. Participants will also complete a series of online surveys that will ask questions about their mental health, which will begin at the time of enrollment, and will be administered at 4 weeks, 8 weeks, and 16 weeks. Participants will receive text message reminders to complete surveys when they are received. Text message reminders will say the following: "Hello, this is a reminder from the Overcoming Thoughts Study to complete your [week 4, 8, 16] surveys. You must complete all surveys in order to receive the maximum payment. (These are very important to our research and we appreciate your time.) If you have any troubles, please contact us. Thank you!" At 16 weeks, an optional follow up remote interview will be conducted with a subset of participants to evaluate acceptability and usability. Researchers will conduct these follow-up interviews with a subset of participants using purposive sampling to identify those who did or not benefit balancing across the treatment and control arm, as well as those who had low and high usage. Benefit will be defined as those who received at least a 25% improvement from pre-treatment score on the DASS and a shift in category (e.g., moderate to mild). Interviewers will be blind to treatment condition as well as benefit and usage status. Each self-report assessment and remote interview will take approximately one hour. The total time required for each participant (including time spent on platform, 4 self-report assessments, and both possible remote interviews) is 10 hours. All remote interviews will be audio recorded for analysis and quality assurance. Researchers will gather usage data directly through the platform, such as number of log-ins and length of use per session.

"Crowduser" information refers to all user-generated responses submitted on the platform, which are subsequently visible to all other users accessing the site. The crowdsourced platform is publicly available on Mental Health America's website, therefore participants in the crowdsource condition may see content submitted by non-study participants. Information submitted by public users (non-participants) will not be gathered and included in the data report that UCI researchers receive. Only data gathered from the consented participants will be gathered for study purposes.

**Feasibility metrics** will also be drawn from data collected through the ADAPT platform including the amount of time required to produce an acceptable response to a request, amount of time between notifications being sent to a user and their login to the platform. If professionals are required to generate some content, we will also estimate the cost of producing a response by tracking professional time and multiplying time by hourly pay rate. Adherence will be tracked as the number of days between a user's first and last login to the ADAPT platform as well as the number of unique days that the user visited the ADAPT platform. Users will be instructed to use the platform at least 3 times a week and we will also look at the number of weeks that users meet this expected level of use (0-8).

**Acceptability** will be assessed through quantitative ratings of the ADAPT platform at end of treatment. Additionally, we will conduct individual interviews with a subset of participants using purposive sampling to identify those who did or not benefit balancing across the treatment and control arm. Benefit will be defined as those who received at least a 25% improvement from pre-treatment score on the DASS and a shift in category (e.g., moderate to mild). Interviewers will be blind to treatment condition as well as benefit status.

**Target Outcomes** include measures of clinical symptoms, accountability, skill use and mastery, functioning, and use of the platform. We will use identical measures to the field trial. An online administered self-report assessment will measure depressive and anxiety symptoms using the DASS, accountability using the SAQ, skills use and mastery using the Frequency of Actions and Thoughts and Coping Self-Efficacy, and functioning using the PROMIS Ability to Participate in Social Roles and Activities Scale at baseline, week 4, week 8, and week 16. A telephone interview will consist of the SCID-5 for depression status and anxiety status at baseline. Use metrics include number of logins, number of times each task is completed (learning, requesting, responding), and time spent on the platform

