
crowdwork, tasks need to be decomposed and distributed such that each person's contribution advances the overall goal of the task. This is possible through structuring intervention content into discrete steps that are consistent with evidence-based treatment strategies. In this project we will evaluate the effectiveness of a crowd-powered treatment for depression and anxiety. The platform will contain structured modules that provide scaffolded instructions for evidence-based treatment strategies (i.e., behavioral experiments and cognitive restructuring) and will support these processes through crowd-interactions. Users of the platform can perform 3 distinct tasks: (1) learning, (2) requesting, and (3) responding. Learning involves reading didactic content, requesting involves completing interactive forms based on the selected treatment strategies, and responding involves interacting with requests submitted by other users. Each user can perform all of these tasks, however, they will be made available on the platform sequentially after each user successfully completes prior tasks. Therefore, users are not assigned to roles from the start but rather will learn, request, and respond at different times. It has been noted that individual psychotherapy as the dominant model of treatment delivery is unlikely to meet the need for mental health services. Instead, we need novel delivery models leveraging new opportunities like technology. The future of BITs for mental health need to include interventions that are as engaging as Facebook and Twitter but as efficacious as the best evidence-based practices developed through years of psychological research. The aim of the current platform is to achieve this goal through combining evidence-based treatment strategies and peer interactions to create a system capable of refining these evidence-based strategies and personalizing mental health interventions.

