## **Power**

We note that RFA-MH-18-706 supports pilot effectiveness research to evaluate the feasibility, tolerability, acceptability, safety and preliminary indications of effectiveness of interventions; to examine whether the intervention engages the target/mechanism that is presumed to underlie the intervention effects; and to obtain preliminary data needed as a pre-requisite to a larger-scale effectiveness trial designed to definitely test the effectiveness of interventions. As such, we are not fully powered on all outcomes. Based on our proposed sample size of 50 participants in the treatment and control conditions, we calculated the effect sizes that we would be able to detect on the primary outcomes using  $\alpha = .05$  and  $\beta = .80$  between treatment (the ADAPT platform) versus control. At this sample size, alpha-level, and power, we would be able to detect an effect size of  $d = .50$  between conditions.

These enrollment targets reflect the minimum targets that we expect and intend to enroll. Given our integration of Mental Health America's Screening-to-Supports (S2S) platform it remains possible that we can recruit a larger number who we might receive partial data on.

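### Does the response-time feasibility metric need a fixed clock and acceptability rule, given that public users' replies stay out of the data?

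*Protocol*

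**What the plan says.** The feasibility paragraph in the Protocol's Methods says its metrics "will also be drawn from data collected through the ADAPT platform". The first is "the amount of time required to produce an acceptable response to a request". The second is "amount of time between notifications being sent to a user and their login to the platform". The sentence after these says that, where professionals have to supply content, the cost of a response will be worked out from their tracked time and hourly pay.

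Earlier in Methods, the paragraph on crowd-user information says the crowd platform is publicly available and that "participants in the crowdsource condition may see content submitted by non-study participants". It then sets a data boundary: "Information submitted by public users (non-participants) will not be gathered and included in the data report" that the researchers receive.

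Scientific Background describes the task itself: "responding involves interacting with requests submitted by other users". It does not limit those other users to trial participants. Under Design, the control platform has neither requesting nor responding, so the metric exists in the treatment arm only.

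The SAP (Statistical Design and Power) contains no analysis of feasibility metrics.

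**The concern.** The metric can be read in two ways. One is effort: the time someone spends writing an acceptable response. The other is waiting: the time from posting a request to receiving its first acceptable reply. The Protocol does not choose between them, does not say who judges acceptability or how, and does not say whether replies from public users or professionals count.

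On the waiting-time reading there seems to be a conflict with the data boundary. If a public user gives the first acceptable reply to a participant's request, the event that stops the clock is not in the research data. An analyst would then have to let the clock run on to the first participant reply, which overstates the wait, or drop the request, which loses data and may select the faster ones. Dropping also requires knowing which requests were affected.

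The stake would be a misleading figure for how quickly the crowd responds. The pilot is meant to inform a larger trial on feasibility, and quick peer response is part of the idea under test.

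**Working it through.** The documents give no figure, target or threshold for this metric, so there is nothing to reproduce. The check sets the texts side by side and then asks how large the bias could be under stated assumptions.

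**1. Is a definition missing?** Yes. The notification metric in the same sentence names both its ends (notification sent, login). The response-time metric names neither. The later paragraph on acceptability concerns ratings of the platform, not the quality of a reply.

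**2. Which reading does the text favour?** The metric is about time needed to *produce* a response, and the following sentence costs the *producing* of a response from time worked. Where the authors mean an interval between two events, they name the events. This leans towards effort time without settling it. On the effort reading, public users' data are not needed for responses written by participants.

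**3. What must hold for the bias to arise?** All of the following:
- waiting time is meant;
- public users reply to participants' requests (inferred from Scientific Background; Methods says only that participants may see public content);
- they reply before any participant gives an acceptable reply;
- their reply is itself acceptable (otherwise the first acceptable participant reply gives the correct time);
- no usable time stamp on the participant's own request is retained.

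The documents establish none of these.

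**4. Size if all of them hold (illustration only).** Assume that acceptable participant and public replies arrive independently, with exponential waiting times at rates λ and μ. Let p be the share of requests whose first acceptable reply is public, so p = μ/(λ + μ).

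*Clock runs on to the first participant reply.* True mean 1/(λ + μ), observed mean 1/λ, ratio (λ + μ)/λ = 1/(1 − p).

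| p | ratio |
|---|---|
| 0% | 1.00 |
| 20% | 1/0.80 = 1.25 |
| 50% | 1/0.50 = 2.00 |
| 80% | 1/0.20 = 5.00 |

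A simulation of one million requests at p = 10%, 25%, 50% and 75% gave 1.109, 1.334, 2.001 and 3.996, against 1.11, 1.33, 2.00 and 4.00 from the formula.

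*Publicly answered requests dropped, all requests alike.* The minimum of two exponentials is independent of which comes first, so the ratio is 1.00 at every p. The cost is the loss of a share p of requests.

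*Dropped, with unlike requests.* Let half the requests have participant rate 1 and half 1/4, with public rate 0.5 for both.
- p = ½(0.5/1.5 + 0.5/0.75) = 0.50.
- True mean = ½(1/1.5 + 1/0.75) = 1.00.
- Probabilities of being kept are 1/1.5 = 0.667 and 0.25/0.75 = 0.333, so the retained mean is (0.667 × 0.667 + 0.333 × 1.333)/(0.667 + 0.333) = 0.889.

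At p = 20% and 80% the ratio is 0.935. With participant rates 1 and 1/2 the ratios are 0.982, 0.971 and 0.982 at p = 20%, 50% and 80%.

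The result can therefore be too slow, correct or slightly too fast. Every input to these ratios is assumed.

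**The case for a change.** The strongest case for a change is that two analysts could report different quantities from the same log, and that a clock chosen after the data are seen could be chosen to flatter the platform. A sentence or two would prevent this. At the planned size ("proposed sample size of 50 participants in the treatment and control conditions"), only 50 − 1 = 49 other participants could give a recorded reply to any one request, while the number of public users is unstated and might be large. A retained time stamp would not show whether a public reply was acceptable.

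Some of this stands. The definition is missing, and on the waiting-time reading a participant-only figure should not be presented as the platform's response time. The rest carries less weight. The count of 49 is not a ceiling, because the SAP's Power section describes its targets as minimums; nor does the count enter the bias ratio, which depends only on p. The scope for a flattering choice is small, since no decision or comparison rests on the result.

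The one remedy that would recover true waiting time is to collect reply times and responder type for public users. It needs an exception to the stated data boundary, the platform host's agreement and probably ethics review. It also needs an acceptability rule that works without reading public text, and the documents do not show that such a rule exists. That is a high price for one descriptive measure.

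**Conclusion.** No change to the plan follows. The gap is real but is one of detail: a secondary, descriptive feasibility measure in one arm is named without its operational definition. Analysts can fill it sensibly from the available log by stating whether they computed effort or waiting time, what counted as acceptable and whose replies were included. If they have only participant replies and use waiting time, an honest label is time to first acceptable reply from a study participant.

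No rule stated in the plan is shown to give a wrong result. The possible distortion runs from none to a several-fold overstatement of mean waiting time (1.25 to 5.00 for p of 20% to 80%). That range rests on the waiting-time reading, exponential waiting times, no usable time stamp and an assumed p about which the documents are silent. It would be too strong to say the metric cannot be measured correctly whenever a public user replies first, because an unacceptable public reply does no harm.

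The DASS comparison and the other feasibility metrics are unaffected. This conclusion would need another look if a go/no-go threshold for a larger trial were attached to the metric; the documents attach none.

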## **Scientific Background:**

Depression and anxiety are the most common mental health disorders in the United States with estimated 12-month prevalence rates of 18.1% and 9.5% respectively. These disorders commonly co-occur and it is estimated that over 70 million Americans each year will meet diagnostic criteria for either depression or anxiety. The human and economic burden of depression and anxiety are monumental. Depression alone is the leading cause of disability and represents the highest disease burden worldwide. Depression and anxiety have comparable impacts on quality of life and are associated with high levels of lost work productivity and increased medical costs. Efficacious treatments exist, yet many people fail to receive them. Estimates of service utilization indicate that among those meeting criteria for a mental disorder nearly 80% receive no treatment whatsoever. Barriers to treatment include costs, time, access, and stigma associated with mental health treatment. In response to these barriers, many researchers and healthcare systems have turned to technology-based treatment options, such as Internet websites and mobile apps, as alternatives to traditional face-to-face treatments. These interventions are referred to collectively as “behavioral intervention technologies” (or BITs) to distinguish them from other information and communication technologies that support healthcare more generally such as electronic medical records, clinical decision support programs, and telemedicine. As an alternative to traditional treatments, BITs allow users to access resources from anywhere in the world, at a time of their choosing. Various BITs for depression and anxiety have been evaluated with evidence supporting their efficacy. This includes Internet websites and mobile applications that draw from established evidence-based treatments such as cognitive-behavioral therapy (CBT), or transdiagnostic approaches. Despite their efficacy, one of the primary challenges that BITs face is sustained engagement. Open access BITs have particularly low rates of adherence with several studies finding only 1% of users complete all modules. Engagement tends to be better in clinical trials of BITs, with a systematic review finding completion rates ranged from 12-100% with a median of 56%. One characteristic that differentiated those trials with higher completion rates from those with lower completion rates was the use of human supported BITs. Completion rates in human supported BITs were found to be 80%, which compares favorably to face-to-face treatment. We think human support matters because it increases personal relevance of the techniques contained within the BIT and increases accountability. In traditional face-to-face CBT, the techniques factor refers to a therapist's fidelity to evidence-based practices while also acknowledging that adaptations must be made for each individual. In BIT treatments, fidelity to evidence-based principles can be very high, as it is pre-programmed. Most BITs, however, are not adapted for an individual and their needs. As such, we suggest that increasing the personal relevance within BIT treatments may increase skills use, mastery, and ultimately functioning. Personal relevance can be increased by including human supporters to clarify the use of the BIT and provide supplemental information to improve fit and use in a person's daily life. Human support also increases relational factors. In traditional face-to-face CBT, relational factors refer to the general qualities of the interaction between patient and therapist, and the therapist's ability to be attuned to their patients. In BIT treatments, relational factors have been most often described through the model of supportive accountability. In short, personally relevant therapeutic techniques and accountability drive skills use and mastery. Increased skills use and mastery results in improved functioning and clinical outcomes. Indeed, a robust literature links CBT skills use and mastery to outcome in therapy. Less research has evaluated what factors increase skills use, but BIT treatments provide a unique opportunity to explore this in detail through their ability to systematically collect data regarding skills use. This conceptual model helps illustrate why BITs that include human support have higher rates of engagement and greater efficacy. In order for BITs to reach their potential of offering scalable accessible interventions, novel strategies are needed to leverage non-professionals to support treatment engagement. This project explores enhancing BITs through crowd-powered processes. Crowdsourcing has been used in several successful technologies (e.g., reCAPTCHA, Foldit). At its core, crowdsourcing is a method for rapidly mobilizing large numbers of people to accomplish tasks on a larger scale. For effective

crowdwork, tasks need to be decomposed and distributed such that each person's contribution advances the overall goal of the task. This is possible through structuring intervention content into discrete steps that are consistent with evidence-based treatment strategies. In this project we will evaluate the effectiveness of a crowd-powered treatment for depression and anxiety. The platform will contain structured modules that provide scaffolded instructions for evidence-based treatment strategies (i.e., behavioral experiments and cognitive restructuring) and will support these processes through crowd-interactions. Users of the platform can perform 3 distinct tasks: (1) learning, (2) requesting, and (3) responding. Learning involves reading didactic content, requesting involves completing interactive forms based on the selected treatment strategies, and responding involves interacting with requests submitted by other users. Each user can perform all of these tasks, however, they will be made available on the platform sequentially after each user successfully completes prior tasks. Therefore, users are not assigned to roles from the start but rather will learn, request, and respond at different times. It has been noted that individual psychotherapy as the dominant model of treatment delivery is unlikely to meet the need for mental health services. Instead, we need novel delivery models leveraging new opportunities like technology. The future of BITs for mental health need to include interventions that are as engaging as Facebook and Twitter but as efficacious as the best evidence-based practices developed through years of psychological research. The aim of the current platform is to achieve this goal through combining evidence-based treatment strategies and peer interactions to create a system capable of refining these evidence-based strategies and personalizing mental health interventions.
